9. STATISTICS

This section provides a summary of the planned statistical analyses; additional detail will be contained in the Statistical Analysis Plan. In any apparent instances of ambiguity or disparity, the terms and procedures of the Statistical Analysis Plan (SAP) govern trial analyses.

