9.1.4 PRIMARY OUTCOME

The intervention (NMP) will be compared against control (SCS) for all primary and secondary outcomes in the mITT population.

Primary outcome, difference in EAD, will be analyzed using a logistic model with adjustment for stratification factors. The hypothesis is:

H0: $EAD_{NMP} \ge EAD_{SCS}$

HA: $EAD_{NMP} < EAD_{SCS}$

In other words, the EAD for the NMP group is less than the EAD for the SCS group.

EAD is a binary outcome defined by the presence of one of the following 3 outcomes [40]:

1. Serum bilirubin ≥ 10 mg/dL at day 7 post-transplant

- 2. International normalized ratio \geq 1.6 at day 7 post-transplant
- 3. ALT or AST > 2000 IU/L within the first 7 days post-transplant

The primary analysis will be a logistic model, adjusted for participating (recipient) center using SAS PROC LOGISTIC or a similar procedure. Significance for the treatment effect will be assessed by the p-value associated with the F-test statistic for the treatment group assignment.

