9.1 Randomization

Donor livers will be randomly assigned to NMP or SCS with 1:1 allocation as per a computer generated randomization schedule using variable block randomization using the following stratification factors: participating (recipient) center and donor type (DBD or DCD). The randomization schedule will be created by the study statistician, and will remain confidential.

Allocation concealment will be ensured by use of central computerized randomization. Allocation will not be revealed until the recipient has been recruited to the trial and donor and recipient inclusion/exclusion criteria have been recorded. Random permuted block length will be used; block sizes will not be disclosed.

Prior to randomization, the local Investigator will confirm the availability of the investigational metra @ device. Once informed consent has been verified from the potential recipient of an organ and recipient and donor inclusion and exclusion criteria has been confirmed, the local recipient investigative site staff will proceed with randomization. Recipients will be considered enrolled in the study once a randomized liver has been assigned and there is an attempt to transplant the randomized liver. An attempt to transplant a liver is considered when there is knife-to-skin contact in the operating room during the recipient transplant procedure. A subject is considered to be transplanted when there is reperfusion of the donor liver in the recipient subject.

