11.2 Missing Data

Endpoints may be missing because results of any of the 3 components of the EAD score are not analyzable, or because subjects have died, refused follow-up, or have withdrawn from the study. Section 12.5.1.3 outlines additional clinical decision techniques that will be used for those enrolled recipients where the endpoint is missing. If EAD is still unable to be determined after using these techniques, imputation methods will be used. Analyses that include imputation for missing data, are considered the standard analyses and will be used to analyze the primary endpoint.

Every effort will be made to obtain information regarding EAD for all recipients. If unavailable, the sponsor will report the reason for recipients with missing endpoint data. If the recipient is missing data and EAD cannot be determined using the additional clinically justified decision rules, the EAD endpoint will be imputed using baseline characteristics (i.e. treatment group, center, and donor type (DCD/DBD) as well as all available components of EAD collected during study follow-up (bilirubin, INR, and ALT/AST). This will be based on multiple imputation via full conditional specification imputation with the variables listed as above with logistic regression (and the endpoint listed last). Individual covariates may be omitted to still allow for

Ver 4.0 09SEP2020

imputation of the endpoint for the full randomized cohort if there are fitting issues with the covariate imputation process. An augmented likelihood approach will be used if there are fitting issues due to the separation or quasi-separation of data points. Imputation will be performed for 100 data sets. In line with multiple imputation, imputed data sets will be appropriately combined to produce a single estimate of treatment effect, along with the associated p-value for the hypothesis test.

Additional sensitivity analyses could include "completers only", last observation carried forward, and/or mixed models.

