11.5 Sensitivity Analysis

As mentioned in section 9.2, there may be instances where a donor type was reported as either DBD or DCD prior to randomization and then after the randomization is assigned, the donor type converts. Also, there may be a scenario where a liver is randomized within a stratification factor that is not actually appropriate for the liver (i.e., randomized in the DBD arm but actually a DCD liver). In both of these instances, subjects will be analyzed for the primary analysis in the original donor type group that the randomization assignment was based on. As a sensitivity analysis, those that switched donor types will be analyzed in the donor type group that they switched to, or those that were inappropriately randomized in the wrong stratification group will be analyzed in the correct donor type group, and the analysis will be re-run. If there is no significant impact on the results, subjects will be analyzed according to their original donor type group for all relevant analyses. A similar approach will be taken to investigate the impact of those donor livers that were randomized to the NMP arm, and needed to be converted to SCS at some point during the transport process. Additionally, sensitivity analyses will be conducted to demonstrate the impact on primary endpoint results using multiple imputation for EAD status that is unable to be confirmed by complete labs or at least 1 lab value meeting criteria for EAD.

12. Statistical Analyses

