12.5.1.3 Data Collection and Analysis Methods

Serum bilirubin at day 7 post-transplant, International normalized ratio at day 7 post-transplant, and ALT or AST within the first 7 days post-transplant (collectively "Lab Values") are all reported on the Inpatient Stay (Day 1 through Day 10 Follow-up) CRF. In the event that a recipient is missing information for the endpoint, the following techniques will be employed to impute the primary endpoint outcome for the recipient:

- a. If day 7 INR is missing and day 6 is available, the day 6 value will be used.
- b. If a recipient has been discharged from hospital prior to day 7 post-transplant and the recipient had complete Lab Values before discharge that did not meet the definition of EAD, the recipient will be considered to not have an EAD event.
- c. If the last INR value recorded for a recipient is less than the threshold for EAD and the recipient has complete Lab Values for all other components of EAD that do not meet the definition of EAD, the recipient will be considered to not have an EAD event. Available follow-up Lab Values must also be below the threshold and no readmissions reported to be considered to not have an EAD event.

The primary analysis will be a logistic model, adjusted for participating (recipient) center using SAS proc logistic or a similar procedure. Significance for the treatment effect will be assessed by the p-value associated with the treatment group assignment.

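### The governing primary model adjusts for center only, yet randomization also stratifies on donor type and SAP 11.5 treats donor type as part of the primary analysis

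*Protocol*

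**What the plan says.** - **Randomization.** SAP 9.1 (and Protocol 6.4.1) assigns livers "using the following stratification factors: participating (recipient) center and donor type (DBD or DCD").
- **Primary model, Protocol 9.1.4.** The first statement is that EAD "will be analyzed using a logistic model with adjustment for stratification factors". A later sentence in the same section is narrower: "The primary analysis will be a logistic model, adjusted for participating (recipient) center using SAS PROC LOGISTIC or a similar procedure".
- **Primary model, SAP 12.5.1.3.** "The primary analysis will be a logistic model, adjusted for participating (recipient) center using SAS proc logistic or a similar procedure".
- **Precedence, Protocol 9.** "In any apparent instances of ambiguity or disparity, the terms and procedures of the Statistical Analysis Plan (SAP) govern trial analyses".
- **Donor-type switches and stratification errors, SAP 11.5.** In these cases "subjects will be analyzed for the primary analysis in the original donor type group that the randomization assignment was based on". The analysis is then repeated with the corrected donor type, and the outcome is used as a rule: "If there is no significant impact on the results, subjects will be analyzed according to their original donor type group for all relevant analyses".
- **Imputation, SAP 11.2.** Missing EAD is imputed from "treatment group, center, and donor type (DCD/DBD") and the available EAD components.
- **Other uses of donor type.** It enters the poolability interaction test at the 0.10 level (SAP 11.4.2) and a subgroup analysis (SAP 12.8).

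**The concern.** Protocol 9.1.4 gives two models for one primary test. The precedence clause settles Protocol against SAP in favor of center only. It cannot settle the SAP against itself: SAP 12.5.1.3 has no donor type in the model, while SAP 11.5 is written as if it were there.

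Two things follow.

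- **Two readings of the primary model.** A borderline result could depend on which sentence is followed. The omitted factor is prognostic on the plan's own figures: Protocol 9.2 cites an EAD rate near 40% in DCD donors against 23% in the cohort that defined EAD. SAP 10 counts on extra power from stratifying by site and does not mention donor type.
- **An almost inert check used as a decision rule.** In a center-only model, changing a donor-type label leaves every subject with a determined EAD exactly as before. The label can act only through the imputation model. The re-run will therefore look reassuring almost by construction, and that result then fixes the grouping for the interaction test and the subgroup, where a wrong label does matter. SAP 11.5 gives no criterion for a significant impact and does not say what follows if there is one.

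**Working it through.** **1. The plan's own sample size.** Inputs from Protocol 9.2 and SAP 10: EAD 25% (SCS) and 10% (NMP), pooled Z-test, one-sided 0.025, power 90%, 1:1. With mean rate 0.175:

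n per arm = [1.960·√(2·0.175·0.825) + 1.282·√(0.25·0.75 + 0.10·0.90)]² / 0.15² = (1.053 + 0.675)² / 0.0225 ≈ 132.8, so 133 per arm and 266 in total.

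Power at 133 per arm is 90.05%, so the stated figure reproduces. Expected events under the plan: 133·0.25 + 133·0.10 ≈ 47.

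**2. Assumptions for comparing the models.** The documents plan no DCD share for this trial. Background figures are 360 of 6,449 transplanted US livers (5.6%, Protocol 2.1.4.4) and 4 of 20 in the pilot (20%, Protocol 2.2). Control EAD is held at 25% overall and 40% in DCD, so DBD control EAD = (0.25 − s·0.40)/(1 − s) for DCD share s. That gives 21.3%, 18.6% and 15.0% at s = 20%, 30% and 40%. Also assumed: 15 centers, center logit SD 0.3, permuted blocks of 2/4/6 within center by donor type, and 266 transplanted out of 356 randomized. Tests are one-sided 0.025 Wald tests.

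**3. Center only against center + donor type.** 10,000 trials per cell with equal centers, 5,000 with unequal centers:

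| DCD share | Power, equal centers | Power, unequal centers |
|---|---|---|
| 20% | 91.6 vs 91.9% | 90.4 vs 90.9% |
| 30% | 91.3 vs 92.1% | 91.6 vs 92.3% |
| 40% | 91.4 vs 92.5% | 91.8 vs 92.8% |

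- Type I error: 2.3-2.6% vs 2.6-3.0% (equal centers); 2.5-2.7% vs 2.8-3.0% (unequal).
- Different verdicts on success under the planned effect: 1.5-2.0% of trials (equal); 1.1-2.3% (unequal).
- Median log odds ratio: −1.17 to −1.19 vs −1.22 to −1.28. The two models estimate slightly different odds ratios.
- Mantel-Haenszel test by center and donor type, equal centers: type I error 2.3-2.4%, power 90.3-91.5%.

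**4. Lower DCD shares and other settings.**
- Shares of 10/20/30%, blocks of 4, 3% of donor types wrong, 2,000 trials per cell: power 92.0 vs 92.0%, 91.4 vs 91.9%, 91.7 vs 92.4%. Verdicts differed in 0.8-1.1% of trials under the planned effect and 0.4-0.6% under the null.
- Shares of 5.6-40%, 4,000 trials per cell: power gain 0.3-1.3 points, verdicts differed in 0.9-1.9%, type I error 2.3-2.7% vs 2.6-2.9%.

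**5. The SAP 11.5 re-run.** Assumed: 30% DCD, 8 of 266 donor types wrong as randomized, logistic imputation on treatment, center and donor type, 100 imputations. There were 150 trials with no missing EAD and 40 each with 2% and 5% missing. Change in the treatment log odds ratio after correcting the labels:

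| Model | EAD imputed | Mean change | Largest |
|---|---|---|---|
| Center only | 0% | 0 | 0 |
| Center only | 2% | 0.003 | 0.012 |
| Center only | 5% | 0.003 | 0.018 |
| Center + donor type | 0-5% | 0.028-0.029 | 0.11-0.18 |

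The standard error is about 0.38, so the mean center-only shift is 0.003/0.38 ≈ 0.8% of one standard error. With donor type in the model it is 0.028/0.38 ≈ 7%.

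A wider run of the center-only model (2-10% missing, 3-10% switched) moved z by 0.01-0.04 on average, at most 0.17. The verdict changed in 2 of 360 trials.

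**6. Where the label does matter.** Relabelling 8 livers at random carried the donor-type interaction across its 0.10 threshold in about 5% of simulated trials.

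**The case against.** The strongest reply is that the operative model is already fixed. The specific sentence in Protocol 9.1.4 and SAP 12.5.1.3 agree on center only, and the SAP governs. The disagreement rate then compares the plan with an alternative. That holds between the two documents, but the precedence clause does not reach the conflict inside the SAP.

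Adding donor type can also be called a preference. The power gain is small, and part of it comes from slightly higher type I error; after adjusting for size it was 0.2-0.6 points at 20-30% DCD, within simulation noise. This stands, and it is why the point is not one of validity.

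Nor would adding donor type make the re-run informative: a shift of about 7% of a standard error would still nearly always pass. This also stands. The decision rule needs its own repair, whichever model is primary.

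SAP 11.5 does not say exactly which analysis is repeated. If the donor-type poolability test were included, the re-run would not be inert. The preceding sentence, however, concerns the primary analysis, and the ambiguity is itself a reason to reword.

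Finally, the change may come too late. SAP 4.0 follows completed enrollment (SAP 12.10.1) and preparation of the 30-day report (SAP 12.6), and EAD is settled by day 7. The fix below allows for this.

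**Conclusion.** The concern holds. The primary model is not described consistently, and SAP 11.5 lets a nearly inert re-run set the donor-type grouping for analyses where grouping counts. The center-only test keeps its type I error near 2.5%, and the sample size of 266 is unaffected.

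Leaving donor type out costs between nothing and about 1.3 points of power over DCD shares of 5.6-40%. The two readings give different verdicts in 0.8-2.3% of simulated trials under the planned effect. These sizes rest on the assumed DCD share, center variation, missing-EAD rate and switching rate. The textual conflict, and the zero movement when no EAD is imputed, rest on none of them. It should be fixed, but it does not threaten the validity of the primary test.

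**What to change.** **If EAD by arm has not yet been analyzed:** name one primary model in SAP 12.5.1.3 and in the second statement of Protocol 9.1.4, with treatment, recipient center and donor type as randomized. Have SAP 11.5 refer to that model and say that it stays primary whatever the corrected-donor-type re-run shows.

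**If it has been analyzed:** keep the center-only model as primary, reword Protocol 9.1.4 and SAP 11.5 to match, and label center + donor type as supportive.

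**In either case:**
- Report the donor-type interaction test and subgroup under both original and corrected donor type, instead of letting the re-run choose.
- State which center enters the model when a liver is reallocated to another site. SAP 9.2 allows this, and SAP 11.5 gives no rule for it.
- Pre-specify the handling of sparse centers, for example by pooling small centers or by a conditional or Mantel-Haenszel analysis stratified by center and donor type.

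**Cost.** No new data and one more model term. It is still a change to the governing primary model late in the trial, so it must be justified and logged. With up to 15 centers and about 47 events, the extra term raises the Wald type I error by about 0.2-0.6 points. A Mantel-Haenszel test avoids that rise, with power about equal to the center-only model or up to 1.3 points below it.

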9.1.5 SECONDARY OUTCOMES

The following endpoints will be considered secondary endpoints for the study and will be summarized using the appropriate analyses described in section 9.1.1:

- 1. To compare graft and subject survival between NMP and SCS livers
- 2. To compare evidence of post-reperfusion syndrome between NMP and SCS livers on transplantation
- 3. To compare biochemical liver function between NMP and SCS livers
- 4. To compare evidence of ischemia-reperfusion injury between NMP and SCS livers
- 5. To compare evidence of biliary complications between NMP and SCS livers
- 6. To assess the feasibility and safety of NMP as a method of organ storage and transportation
- 7. To compare organ utilization between NMP and SCS livers
- 8. To assess the health economic implications of normothermic liver perfusion

Additionally, a logistic model will be used to examine the possible explanatory effects of baseline subject characteristics (in the presence of the treatment indicator variable), namely: race, age, gender, and number of liver transplants received (primary or secondary).

Secondary analysis may be stratified by recipient center and donor type (DBD or DCD) for exploratory purposes.

9.1.6 SAFETY ANALYSES

Safety data will be collected and reported on for those recipients that are matched to a randomized liver and there is an attempt to transplant the randomized liver.

9.1.7 SUBGROUP ANALYSES

Subgroup analyses will be performed for donor type (DCD vs. DBD), by donor risk index (DRI), and by duration of machine preservation in the NMP arm of the trial.

Full details of the proposed statistical analysis will be outlined in a separate Statistical Analysis Plan (SAP).

9.1.8 POOLABILITY ANALYSIS

Poolability analyses will be performed on the primary endpoint to assess whether results are poolable across participating centers.

A logistic model with EAD as the dependent (outcome) variable will be reported using a binary treatment indicator variable and site by treatment interaction term(s) as independent variables to assess poolability of data across sites. Absence of statistically significant interaction term(s) (using a p-value of 0.1 as the cut-off) will be taken as evidence of poolability across the sites. Any interaction term that is statistically significant will trigger an examination of the data at the relevant site to determine the underlying reason(s). Since the power associated with testing for a significant interaction is likely to be low, the difference between the two treatment groups will be reported descriptively for each investigational site. A similar approach will be used to assess poolability across donor types.

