9.3 Blinding

While it is not possible to blind the local Investigators to the method of organ preservation, Histopathologists at the central laboratory interpreting the biopsy specimens will remain blinded to the randomization group to the extent possible.

10. Sample Size Considerations

Power calculations of the superiority of NMP versus SCS were based on a test of inequality for two proportions using a pooled Z-test and one-sided α =0.025.

The following assumptions were considered:

EAD_{NMP}=10%

EAD_{SCS}=25%

Based on the above assumptions, it is estimated that 266 (approximately 356 total sample size considering approximately 25% attrition) transplanted livers will provide 90% overall power. Power calculations were conducted using PASS 14. Power for the primary analysis based on logistic regression is similar to this, and stratification based on sites will provide additional power if site is prognostic.

11. Data Structure and Handling

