11.4 Pooling of Data

11.4.1 Across Trial Sites

Up to 15 sites will enroll recipients in the study. Statistical investigation of the homogeneity of results across investigational sites will be performed in order to ensure the poolability of results to address the primary endpoint. Statistical analyses used to assess the site by treatment interaction will be tested at a significance level of p=0.10.

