11.4.2 Across Donor Types

Livers received from both DBD and DCD donors will be included in this study. Statistical investigation of the homogeneity of results across donor type will be performed in order to

ensure the poolability of results to address the primary endpoint. Statistical analyses used to assess the donor type by treatment interaction will be tested at a significance level of p=0.10.

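### The poolability models list treatment and interaction terms but no site or donor-type main effect, so as written the test mixes prognosis with differences in treatment effect

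*Protocol*

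**What the plan says.** Protocol 9.1.8 specifies a logistic model with EAD as outcome that "will be reported using a binary treatment indicator variable and site by treatment interaction term(s) as independent variables". For donor type it adds: "A similar approach will be used to assess poolability across donor types". If no interaction term reaches the 0.10 cut-off, the data count as poolable. A significant term leads to an examination of the data at that site. The section concedes low power and promises a descriptive treatment difference for each site.

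The opening of Protocol section 9 lets the SAP govern where the two documents are ambiguous or disagree. SAP 11.4.1 says only: "Statistical analyses used to assess the site by treatment interaction will be tested at a significance level of p=0.10". SAP 11.4.2 says: "Statistical analyses used to assess the donor type by treatment interaction will be tested at a significance level of p=0.10". Neither lists model terms.

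The documents are not consistent about donor type in the primary model. Protocol 9.1.4 first says the outcome "will be analyzed using a logistic model with adjustment for stratification factors", which would include donor type. SAP 11.5 says that, where donor type was switched or misassigned, "subjects will be analyzed for the primary analysis in the original donor type group that the randomization assignment was based on". Yet SAP 12.5.1.3 reads: "The primary analysis will be a logistic model, adjusted for participating (recipient) center using SAS proc logistic or a similar procedure". Protocol 9.1.4 closes the same way, with center alone.

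**The concern.** An interaction term measures a difference in treatment effect only if the model also contains the main effect of the factor. Without it, any difference in EAD risk between sites or donor types is pushed into the interaction term.

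The documents allow for such differences. Protocol 9.2 cites EAD near 40% in DCD donors, against 23% in an overall US cohort. SAP section 10 says that "stratification based on sites will provide additional power if site is prognostic". Randomization is stratified by both factors.

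Two errors are possible. A uniform treatment effect can be flagged as heterogeneous, which starts an unneeded data examination. Under one coding, real heterogeneity can be hidden and the data declared poolable.

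**Working it through.** **Baseline from the plan.** For 25% against 10%, one-sided 0.025, 90% power and a pooled Z-test:

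n per arm = [1.960·√(2·0.175·0.825) + 1.282·√(0.25·0.75 + 0.10·0.90)]² / 0.15² = 132.8, so 133 per arm and 266 in total. This reproduces the plan's figure and is not in dispute. The planned effect is an odds ratio of (0.10/0.90)/(0.25/0.75) = 1/3.

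**What the listed model tests.** Let T be the 0/1 treatment indicator and D = 1 for DCD.

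- Full model: logit p = a + bT + δD + γTD. Here δ is prognosis and γ is the interaction.
- Listed model: logit p = a + bT + cTD.

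In the listed model every liver with T = 0 has log-odds a, whatever its donor type. The coefficient c is the DCD-minus-DBD log-odds contrast among livers with T = 1. The likelihood-ratio test of c is therefore a comparison of EAD by donor type inside that one arm, to which the other arm contributes nothing.

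- NMP coded 1: c = δ + γ.
- SCS coded 1: c is the DCD–DBD contrast in the SCS arm, which is prognosis alone.

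The same holds for J sites, with J − 1 contrasts inside one arm.

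**Worked case, 20% DCD share.** 133 × 0.2 gives about 27 DCD and 106 DBD livers per arm. SCS odds are 0.23/0.77 = 0.299 (DBD) and 0.40/0.60 = 0.667 (DCD), so the prognostic odds ratio is 2.23. With odds ratio 1/3 in both types, the NMP rates are 9.1% and 18.2%. Here γ = 0, but c = ln 2.23 = 0.80.

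**Donor type: false-flag rate at 0.10 with a uniform treatment odds ratio** (20,000 simulated trials per scenario, likelihood-ratio test)

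| DCD share | NMP = 1 | SCS = 1 | +1/−1 | With main effect |
|---|---|---|---|---|
| 10% | 26% | 36% | 20% | 13% |
| 20% | 37% | 53% | 21% | 11% |
| 30% | 44% | 62% | 22% | 11% |

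If EAD under SCS is 25% in both types, the listed model gives 10–16% under every coding, against 11–14% with the main effect. At 20% DCD share, with DCD held at 40% and DBD EAD of 20/25/30/35%, the rates are:

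- NMP = 1: 45/31/21/14%
- SCS = 1: 67/44/26/14%
- +1/−1: 26/19/14/12%
- with the main effect: 11%

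**Masking.** Suppose NMP brings both types to 10%. The treatment odds ratios are 0.111/0.299 = 0.37 (DBD) and 0.111/0.667 = 0.17 (DCD), a real interaction. With NMP = 1, c is zero. At 20% DCD share the listed test flags 12%, against 28% with the main effect. SCS = 1 flags 54% and +1/−1 flags 45%, so masking is confined to NMP = 1.

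**Sites: joint likelihood-ratio test, no true interaction, SCS EAD 25%, 5/8/15 equal sites** (10,000 trials per scenario)

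| Between-site logit SD | NMP = 1 | SCS = 1 | +1/−1 | With site main effects |
|---|---|---|---|---|
| 0.25 | 21/22/19% | 21/22/26% | 12/12/13% | 15/17/20% |
| 0.5 | 37/36/30% | 49/47/49% | 16/15/15% | 15/16/18% |
| 1.0 | 70/73/72% | 85/89/90% | 23/19/15% | 13/14/13% |

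An SD of 0.5 means SCS EAD of about 17% to 35% at ±1 SD. With no between-site variation there is no excess over the corrected model under any coding.

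**Assumptions not in the documents:** DCD share, 23% as the DBD rate (it is an overall-cohort figure), a uniform odds ratio of 1/3, the coding, the number of sites (the plan says up to 15) and their size, and the between-site SD.

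**The case against.** The strongest reply is that the list is shorthand. Protocol section 9 calls itself a summary and yields to the SAP, which asks for tests of the site-by-treatment and donor-type-by-treatment interactions. Most statisticians would include the lower-order terms without being told. For sites, the primary model already adjusts for center, so adding an interaction to it would be natural.

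Little depends on the result. A false flag costs a look at the data, site differences are reported descriptively whatever the p-value, and a donor-type subgroup analysis is planned anyway.

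The sizes also rest on assumed inputs. DBD donors must be at least 40 while DCD donors may be 16, and the protocol lists age as a risk factor, so the DBD–DCD gap may be narrower than 23% against 40%. With 15 sites and SD 0.25, the listed model with NMP = 1 does no worse than the corrected one (19% against 20%).

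Much of this stands. The intent is probably a proper interaction test, the consequence is small, and the percentages apply only to a literal fit. But SAP 11.4 names no terms, so its precedence corrects nothing, and neither document says the poolability model extends the primary model. For donor type, borrowing from the primary model is unsafe because the documents disagree on whether donor type is in it.

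**Conclusion.** The concern holds as a minor point: the model as written tests the wrong quantity. Fitted literally with a 0/1 indicator, the donor-type test flags a uniform treatment effect in 26–44% (NMP = 1) or 36–62% (SCS = 1) of trials over DCD shares of 10–30%, against 11–13% with the main effect. For sites at logit SD 0.5 the rates are 30–37% and 47–49%, against 15–18%.

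The excess needs a prognostic factor. It shrinks as the DBD and DCD rates converge. With +1/−1 coding there is no material excess for sites at SD 0.5, while donor type still runs at 20–22%. The damage is limited to the poolability statement and the examination it triggers. The primary test, alpha, sample size and success criterion do not change.

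**What to change.** State the terms, the test and the treatment coding:

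- SAP 11.4.1: treatment, site and site-by-treatment, with a joint test of the interaction at 0.10.
- SAP 11.4.2: treatment, donor type and donor-type-by-treatment, with the interaction tested at 0.10.

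The SAP governs, so this wording is sufficient. Protocol 9.1.8 should be aligned with it for consistency. Keep the descriptive site differences.

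The cost is one sentence in each SAP section. The donor-type model gains one parameter and the site model up to 14. The corrected site test still runs at about 15–21%, not 10%, when site differences are absent or moderate (SD 0 to 0.5), because 15 sites leave about 9 livers per site and arm (133/15). Combining small sites by a rule based on enrollment counts alone, or using a penalized test, would address that. It is a separate refinement, and the main-effect correction does not depend on it.
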